4.1.3.2 Dose-limiting toxicities

For definition of a DLT, it is essential that patients are treated sufficiently according to supportive care standards, and baseline conditions, coexisting symptoms, and/or transient laboratory abnormalities of patients are also considered. A drug-related adverse event constitutes a DLT, if one of the following applies during Cycle 1:

Haematological toxicities:

- CTCAE grade 4 neutropenia (neutrophil counts of $<500/\mu\text{L}$) lasting 7 or more days
- Febrile neutropenia (neutrophil counts of $<1000/\mu\text{L}$ with once observed a temperature of $\geq38.3^\circ\text{C}$ or a sustained temperature of $\geq38.0^\circ\text{C}$ for more than 1 hour)
- Infection with neutrophil counts of $<1000/\mu\text{L}$
- CTCAE grade 4 thrombocytopenia (platelet counts of $<25\,000/\mu\text{L}$) or CTCAE grade 3 thrombocytopenia (platelet counts of $<50\,000\text{--}25\,000/\mu\text{L}$) associated with bleeding requiring platelet transfusion

Non-haematological toxicities:

- CTCAE grade 3 or 4 non-haematologic toxicity (except incompletely treated nausea, untreated vomiting, untreated diarrhoea, skin toxicity, fatigue, infusion reaction, electrolyte, hyperglycaemia, AST, or ALT). The following drug-related non-haematological toxicities should be defined as DLTs:
 - CTCAE grade ≥ 2 infusion reaction despite adequate pre-medication
 - CTCAE grade ≥ 2 nausea and/or vomiting persisting for 7 or more days despite antiemetic treatment
 - CTCAE grade ≥ 3 skin toxicity despite adequate supportive care measures for up to 14 days if it does not reach an improvement to grade ≤ 2
 - CTCAE grade ≥ 3 hyperglycaemia resistant to treatment with anti-diabetic agents
 - Any electrolyte CTCAE grade 3 adverse event which is refractory to optimal correction therapy
 - No recovery from a non-DLT CTCAE grade ≥ 3 toxicity to grade ≤ 1 within 14 days of administered dose
 - Sustained CTCAE grade 3 fatigue or asthenia for longer than 96 hours associated with deterioration of ECOG performance status

It is understood that also other drug-related adverse events (CTCAE grade 2) may carry the potential to be significant enough to necessitate treatment interruption or discontinuation, and as such qualify as DLT. Such adverse events will be required the confirmation after thorough discussion between the investigator and the sponsor on a case-by-case basis.

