All adverse events which are determined as DLTs occurring during Cycle 2 or later (DLT-equivalent adverse events) will also be considered during evaluation of the overall safety in the trial.

All DLTs and DLT-equivalent adverse events have to immediately be reported to the sponsor. DLTs and DLT-equivalent adverse events must be determined after discussion and agreement with the investigator and the sponsor. The sponsor may ask for the opinion of the assigned external expert if needed.

[figure not shown]

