4.1.3.3 Maximum tolerated dose

The MTD of BI 836845 is the highest dose tested with DLT occurring in not over 1 out of 6 evaluable patients.

In case the MTD will not be reached until 1400 mg, it will be deemed as a sufficient tolerability in Japanese patients with advanced solid tumours at 1400 mg.

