4.1.3.4 Dose escalation, cohort expansion, and/or dose de-escalation

Dose escalation, cohort expansion, and/or dose de-escalation will be performed as summarised in Figure 4.1.3.4: 1.

i

[figure not shown]
[figure not shown]
iii

←

ii

iv

←

a. Three (3) evaluable patients will be entered into the de-escalated dose cohort. It cannot be decided the dose re-escalation from the de-escalated dose cohort.
b. Patient entry will be finished if 6 evaluable patients have already been entered into the de-escalated dose cohort.

Figure 4.1.3.4: 1 Criteria for dose escalation, cohort expansion, and dose de-escalation

In case no MTD can be identified up to the highest dose tested in this trial, additional 6 patients may also be entered as an expansion cohort to be recommended a relevant biological dose.

Dose escalation, cohort expansion, or dose de-escalation must be decided after discussion and agreement with the principal investigator and the sponsor based on the incidence of all reported DLTs. The sponsor may ask for the opinion of the assigned external expert if the investigator or the sponsor considers this to be needed.

4.1.3.5 Initiation of study treatment with BI 836845 for the next cycle (Cycle 2 onwards)

Except for the rollover part, patients who met all of the following criteria on the first day planned to initiate the study treatment of next cycle will continue the study treatment and will perform the assessments defined for Day 1 of next cycle.

- Recovery of drug-related haematological adverse events to CTCAE grade ≤2 or baseline
- Recovery of drug-related non-haematological adverse events to CTCAE grade ≤1 or baseline (except for alopecia, skin hyperpigmentation, incompletely treated nausea, untreated vomiting, untreated diarrhoea, skin toxicity, fatigue, infusion reaction, electrolyte, hyperglycaemia, AST, or ALT)
- Absence of any other discontinuation criteria (see [Section 3.3.4](#))
- Written re-consent for the participation of repeated study treatment from Cycle 2 (only before start of Cycle 2)

Patients who are not eligible for continuing the study treatment will discontinue the study treatment and will be assessed at EOT visit.

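### Only fatigue is exempt from the general grade 3–4 criterion, so every drug-related grade 3 asthenia in Cycle 1 is a DLT, while the same event recorded as fatigue need not be

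*Protocol*

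**What the plan says.** Protocol Section 4.1.3.2 first states how the criteria combine: "A drug-related adverse event constitutes a DLT, if one of the following applies during Cycle 1". Each criterion is thus sufficient by itself.

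The first non-haematological criterion takes in all grade 3 or 4 events, "except incompletely treated nausea, untreated vomiting, untreated diarrhoea, skin toxicity, fatigue, infusion reaction, electrolyte, hyperglycaemia, AST, or ALT". Asthenia is not in that list. Sub-bullets then define when particular toxicities count. The last one handles two terms together: "Sustained CTCAE grade 3 fatigue or asthenia for longer than 96 hours associated with deterioration of ECOG performance status".

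The section also provides that "DLTs and DLT-equivalent adverse events must be determined after discussion and agreement with the investigator and the sponsor", and Section 3.1.1 adds review by an independent external expert. Section 4.1.3.3 turns the count into the primary result: "The MTD of BI 836845 is the highest dose tested with DLT occurring in not over 1 out of 6 evaluable patients". SAP Section 7.4 refers back to Protocol Section 4.1.3.2 for the definition of a DLT and adds nothing on this point. The next-cycle criteria in Protocol Section 4.1.3.5 carry a similar exception list, again with fatigue and without asthenia.

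**The concern.** The last bullet treats fatigue and asthenia as one kind of event and asks for both duration and functional decline before it counts. The exemption that would let those conditions operate was given to only one of the two terms. Two near-synonyms therefore fall under different rules, and nothing in the Protocol or SAP says that fatigue includes asthenia.

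The DLT count is the only basis of the primary endpoint. DLT status also triggers the dose-reduction rule (Section 4.1.3.6) and expedited reporting as an adverse event of special interest (Section 5.2.2.1), and it determines what the report tabulates (SAP Sections 7.4 and 7.8.1). In cohorts of three to six patients, a single classification can decide the outcome.

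**Working it through.** **Step 1: classify one event under both criteria.** Take a drug-related grade 3 event in Cycle 1. The general criterion is met if the term is not exempt. The bullet is met if the event lasts longer than 96 hours and ECOG status deteriorates. The event is a DLT if either is met.

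| Duration, ECOG deterioration | Fatigue: general / bullet / DLT | Asthenia: general / bullet / DLT |
|---|---|---|
| 48 h, no | no / no / **no** | yes / no / **yes** |
| 48 h, yes | no / no / **no** | yes / no / **yes** |
| 120 h, no | no / no / **no** | yes / no / **yes** |
| 120 h, yes | no / yes / **yes** | yes / yes / **yes** |

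The terms give different answers in 3 of 4 cases. For asthenia the answer is always yes, whatever the bullet says. The comparison covers these two criteria only. A fatigue that escapes both could still become a DLT under the separate bullet on non-recovery within 14 days.

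**Step 2: compare with the other sub-bullets.** Infusion reaction, nausea, vomiting, skin toxicity, hyperglycaemia, electrolyte events and fatigue each have a sub-bullet and a matching entry in the exemption list. Asthenia is the only named toxicity with a sub-bullet and no entry.

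**Step 3: effect on the MTD rule.** The plan's only sample-size figure, 18 evaluable patients (3 cohorts × 6), is unaffected. The rule allows at most 1 DLT in 6, so one such event can turn 1/6 (passes) into 2/6 (fails). The escalation figure is not available in the text, so only this rule is used.

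With a per-patient DLT probability p, P(at most 1 of 6) = (1 − p)^6 + 6p(1 − p)^5. The documents give no rates; those below are assumptions. The asthenia rate means grade 3 drug-related asthenia that is short or without ECOG deterioration, and it is added to the rate of other DLTs.

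- 2% other DLTs: 0.98^6 + 6 × 0.02 × 0.98^5 = 0.994. Adding 1% asthenia (p = 0.03): 0.988.
- 10% other DLTs: 0.9^6 + 6 × 0.10 × 0.9^5 = 0.531 + 0.354 = 0.886. Adding 5% asthenia (p = 0.15): 0.377 + 0.399 = 0.776.

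If the two kinds of event are taken as independent, p = 1 − (1 − a)(1 − b). At 10% other DLTs, the probability is then 0.886, 0.868, 0.829, 0.788 and 0.680 for asthenia rates of 0, 1, 3, 5 and 10%. Over the same 0–10% range it goes from 0.967 to 0.788 at 5% other DLTs, and from 0.776 to 0.570 at 15%.

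**Step 4: how likely is the event?** Section 1.4 reports that drug-related events were mostly grade 1 or 2. One severe drug-related event occurred in trial 1280.1, a pulmonary haemorrhage. With the 48 patients given there for that trial, this is 1/48 = 2.1%. No DLT occurred in trial 1280.2. The low-rate scenario is closer to this experience. Even so, no severe drug-related asthenia in 48 patients does not exclude a 5% rate: 0.95^48 = 0.085.

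**The case against.** The strongest reply is that the text does not contradict itself. A reader might infer that a 48-hour grade 3 asthenia both is and is not a DLT. The documents do not support that: the criteria are alternatives, and the bullet never says that a shorter event is not a DLT. It is merely unmet. Read literally, the event has one classification, DLT. This stands; what remains is unequal treatment of two terms and a bullet that has no effect for one of them.

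A reader might also infer that the MTD hangs on the word the investigator records. That goes too far. Each DLT needs agreement between investigator and sponsor, an external expert reviews DLT evaluation, and Section 4.1.3.2 asks that baseline conditions and coexisting symptoms be considered. But none of these steps gives a criterion for asthenia, and the trial is open-label, so a case may be discussed with the cohort's count already known.

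It can further be argued that fatigue is a short label which the bullet spells out, as with electrolyte events. That reading is possible, but it is stated nowhere. Finally, the literal reading counts more DLTs, not fewer, so it does not hide toxicity. That is correct.

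**Conclusion.** The mismatch is real and lies in the rule behind the primary endpoint. As written, the 96-hour and ECOG conditions do nothing for asthenia, and the two terms part in 3 of 4 duration and ECOG combinations. The practical size is uncertain and probably small: a drop of 0.006 in the chance of at most one DLT in six at low assumed rates, and 0.11 at high ones. Both figures assume a full cohort of six and that all the asthenia counted is of the kind the two terms classify differently.

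That general disorders are among the commonest adverse events in Section 1.4 might be read as showing that such cases are likely. It does not: the class is broad, the statement covers all adverse events regardless of cause, and drug-related events were mostly grade 1 or 2. The documents do not show which classification was intended, and this point takes no position on it.

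**What to change.** The sponsor should reconcile the exemption list and the last bullet of Section 4.1.3.2 so that fatigue and asthenia are classified by one and the same rule. Deleting asthenia from the bullet alone would not achieve this: asthenia would still always count while fatigue stayed exempt. The parallel list in Section 4.1.3.5 should be checked at the same time. The clinical trial report should state which reading was applied to any grade 3 fatigue or asthenia in Cycle 1. If DLT evaluation is already complete, that statement is the part that still matters.

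Aligning the terms takes a few words in the Protocol and one sentence in the report, with no added procedures or patients. Any change that goes beyond aligning them would alter the DLT definition, and should be presented as such.

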4.1.3.3 Maximum tolerated dose

The MTD of BI 836845 is the highest dose tested with DLT occurring in not over 1 out of 6 evaluable patients.

In case the MTD will not be reached until 1400 mg, it will be deemed as a sufficient tolerability in Japanese patients with advanced solid tumours at 1400 mg.

4.1.3.4 Dose escalation, cohort expansion, and/or dose de-escalation

Dose escalation, cohort expansion, and/or dose de-escalation will be performed as summarised in Figure 4.1.3.4: 1.

i

[figure not shown]
[figure not shown]
iii

←

ii

iv

←

a. Three (3) evaluable patients will be entered into the de-escalated dose cohort. It cannot be decided the dose re-escalation from the de-escalated dose cohort.
b. Patient entry will be finished if 6 evaluable patients have already been entered into the de-escalated dose cohort.

Figure 4.1.3.4: 1 Criteria for dose escalation, cohort expansion, and dose de-escalation

In case no MTD can be identified up to the highest dose tested in this trial, additional 6 patients may also be entered as an expansion cohort to be recommended a relevant biological dose.

Dose escalation, cohort expansion, or dose de-escalation must be decided after discussion and agreement with the principal investigator and the sponsor based on the incidence of all reported DLTs. The sponsor may ask for the opinion of the assigned external expert if the investigator or the sponsor considers this to be needed.

4.1.3.5 Initiation of study treatment with BI 836845 for the next cycle (Cycle 2 onwards)

Except for the rollover part, patients who met all of the following criteria on the first day planned to initiate the study treatment of next cycle will continue the study treatment and will perform the assessments defined for Day 1 of next cycle.

- Recovery of drug-related haematological adverse events to CTCAE grade ≤2 or baseline
- Recovery of drug-related non-haematological adverse events to CTCAE grade ≤1 or baseline (except for alopecia, skin hyperpigmentation, incompletely treated nausea, untreated vomiting, untreated diarrhoea, skin toxicity, fatigue, infusion reaction, electrolyte, hyperglycaemia, AST, or ALT)
- Absence of any other discontinuation criteria (see [Section 3.3.4](#))
- Written re-consent for the participation of repeated study treatment from Cycle 2 (only before start of Cycle 2)

Patients who are not eligible for continuing the study treatment will discontinue the study treatment and will be assessed at EOT visit.

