3.3.3 Exclusion criteria

Patients for whom any of the following exclusion criteria apply by the judgment of investigator are not eligible to receive the study treatment:

1. Active infectious disease to be incompatible with the study treatment according to the CTP
2. Patients who do not have sufficient major organ function and meet any of the following test results at screening period
 - Cardiac left ventricular function with resting ejection fraction $\leq 50\%$ as determined by echocardiography (ECHO) or multiple-gated acquisition scan (MUGA)
 - Absolute neutrophil count $< 1500/\mu\text{L}$
 - Platelets $< 100\,000/\mu\text{L}$
 - Total bilirubin $> 1.5 \times$ the upper limit of normal (ULN)
 - AST (SGOT) and/or ALT (SGPT) $> 2.5 \times$ ULN (in case of known liver metastases, AST and/or ALT $> 5 \times$ ULN)
 - Creatinine $> 1.5 \times$ ULN
 - Haemoglobin $< 9\text{ g/dL}$
 - HbA_{1c} $\geq 8\%$ and fasting glucose $> 8.9\text{ mmol/L} (> 160\text{ mg/dL})$
3. Serious illness or concomitant non-oncological disease including severe, acute, or chronic medical or psychiatric condition, or laboratory abnormality that may compromise the safety of the patient during the study, affect the patient's ability to complete the study, or interfere with interpretation of study results considered by the investigator to be incompatible with the study treatment according to the CTP
4. History of thrombosis (except tumour invading great vessels) within 1 year before start of study treatment or if concurrent anticoagulation required
5. Patients not recovered from any therapy-related toxicities from previous chemotherapies, hormonal therapies, immunotherapies, molecular-targeted therapies, or radiotherapies to CTCAE grade ≤ 1
6. Patients who have not recovered from any previous surgery and major surgery within the last 4 weeks before start of study treatment
7. Patients with untreated or symptomatic brain metastases. Patients with treated asymptomatic brain metastases may be eligible if there has been no change in brain disease status for at least 4 weeks before start of study treatment, no history of cerebral oedema or bleeding in the past 4 weeks before start of study treatment, and must be on a stable or reducing dose of dexamethasone. Anti-epileptic therapy will be allowed during the study treatment if the patient is stable on antiepileptic treatment for 4 weeks or more without adjustments before start of study treatment.

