3.3.4.1 Criteria for discontinuation of study treatment in the trial for individual patients

Patients should discontinue the study treatment and initiate EOT and subsequent visits if any one of the following criteria is met:

Proprietary confidential information © 2024 Boehringer Ingelheim International GmbH or one or more of its affiliated companies

- Patients who withdraw consent to further study treatment
- Patients who are no longer able to continue the study treatment (e.g. undue toxicity, pregnancy, surgery, concomitant diagnoses, concomitant therapies, administrative reasons) after discussion and agreement with the investigator and the sponsor
- Patients who developed PD by the discretion of investigator
- Patients who interrupt the study treatment more than 4 weeks as counted from the next planned treatment administration. If an interruption of more than 4 weeks is necessary and clinically justified, the patient may continue the study treatment after discussion and agreement between the investigator and the sponsor if there is documented clinical benefit (e.g., SD, disease control).
- Patients who require more than 2 dose reductions or dose reduction less than 500 mg throughout the study treatment

The EOT visit should be performed within 5 days after discontinuation of study treatment except for the rollover part. In case an adverse event is still ongoing at the time of discontinuation, every effort should be made to follow-up for the adverse event according to [Section 5.2.2.2](#).

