6.2.3 Treatment period

All assessments and evaluations must be performed before infusion of BI 836845 except for a part of vital signs, ECG measurements, and pharmacokinetic blood samplings (see [Flow Chart](#)).

The investigator confirms whether inclusion and exclusion criteria are still valid or not before study treatment on Visit 1 of Cycle 1. For patients who are willing to continue the study treatment after completion of Cycle 1, written informed re-consent must be obtained before study treatment on Visit 1 of Cycle 2.

All planned visit dates are programmed from the start of Day 1 of Cycle 1. If a visit is missed, there will be no re-scheduling. If a patient should attend the trial site between the “missed” and the next scheduled visit, the missed visit assessments should be performed. The current date and the reason for the delay must be recorded in the medical records. All subsequent visits should adhere to the scheduled visits for all cycles of treatment period.

The treatment period of the trial will continue for an indeterminate number of cycles until any one of discontinuation criteria (see [Section 3.3.4.1](#)) is met, and then the EOT visit must be performed. The end of treatment period will be the last day of study treatment.

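### Protocol 4.1.3.5 exempts isolated AST/ALT rises and hyperglycaemia from the start-of-cycle check with no upper grade, so only judgement holds the Day 1 infusion for a new drug-related grade 3 or higher event

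*Protocol*

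**What the plan says.** Section 4.1.3.5 lists the conditions for starting Cycle 2 and every later cycle outside the rollover part. Patients who meet all of them continue treatment.

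- Drug-related haematological events must be at grade 2 or lower, or at baseline.
- Drug-related non-haematological events must be at grade 1 or lower, or at baseline, "except for alopecia, skin hyperpigmentation, incompletely treated nausea, untreated vomiting, untreated diarrhoea, skin toxicity, fatigue, infusion reaction, electrolyte, hyperglycaemia, AST, or ALT". No grade cap, time limit or substitute threshold is given for the listed terms.
- The third condition is "Absence of any other discontinuation criteria", with a reference to 3.3.4.
- For those who fail: "Patients who are not eligible for continuing the study treatment will discontinue the study treatment and will be assessed at EOT visit".

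Section 4.1.3.2 uses a nearly identical exception list in its grade 3 or 4 DLT rule, then adds specific conditions for several of the exempt terms. For glucose, the condition is grade 3 or higher "hyperglycaemia resistant to treatment with anti-diabetic agents". AST/ALT has no bullet of its own. A general clause makes any non-DLT toxicity of grade 3 or higher a DLT if it has not returned to grade 1 or lower "within 14 days of administered dose".

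**The concern.** Read as written, the check is uneven. A drug-related grade 2 event that is not on the list, and is above baseline, fails it and ends treatment. A new isolated grade 3 or 4 ALT rise passes.

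The protocol does set numeric limits for the same tests before the first dose. Exclusion criterion 2 bars AST/ALT above 2.5 x ULN, with a looser 5 x ULN limit "in case of known liver metastases, AST and/or ALT". It also bars HbA1c of at least 8% with fasting glucose above 160 mg/dL. Those limits are rechecked only once: "The investigator confirms whether inclusion and exclusion criteria are still valid or not before study treatment on Visit 1 of Cycle 1". Nothing comparable applies at later cycle starts.

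The stake is patient safety at one decision point. Section 2.3 lists hyperglycaemia and raised transaminases among the effects of anti-IGF-1R agents and calls the risks in Japanese patients unknown. The half-life is about 6 days (1.4), and no agent reverses the drug's effects (4.2.1). From Cycle 4 the Flow Chart schedules laboratory tests only at Visit 1, so the Day 1 check is then the only scheduled laboratory checkpoint in the cycle.

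**Working it through.** **Step 1. Which rules can hold the Day 1 infusion?** The events considered are drug-related, grade 3 or higher, new at a cycle start and not yet DLT-equivalent.

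| Protocol section | Isolated AST/ALT rise | Hyperglycaemia not yet shown to respond |
|---|---|---|
| 4.1.3.5, recovery criterion | Exempt | Exempt |
| 4.1.3.5, third criterion, via 3.3.4.1 | Undue toxicity: judgement, no grade | Same |
| 4.1.3.2, specific bullet | None | Only once resistant to treatment |
| 4.1.3.2, non-recovery clause | Only after 14 days | Only after 14 days |
| 4.1.3.2, closing paragraph | Case by case; literally names grade 2 | Same |
| 4.1.3.6 | Only for a DLT or DLT-equivalent event | Same |
| 4.1.3.7 | Interruption allowed for safety concern; no grade | Same |
| 5.2.2.1, DILI | Needs bilirubin of at least 2 x ULN in the same sample; dosing refers back to 4.1.3.5, 4.1.3.6 and 4.2 | Not applicable |
| 4.2.1.2 | Not applicable | Glucose treatment; no limit for holding study drug |

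No row gives a grade-based hold on Day 1 for either event. Flow Chart footnote 13 (more frequent testing at discretion) and 5.2.2.2 (follow-up to grade 1 or baseline) do not hold a dose either.

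**Step 2. When does the 14-day clause mature?** Doses fall on Days 1, 8 and 15 of a 21-day cycle, so the next cycle's doses fall on Days 22, 29 and 36. Limit = day of the dose that starts the clock + 14. For an event already present on Day 22, the clock starts at an earlier dose, but the text does not say which.

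- From the Day 8 dose: 8 + 14 = Day 22. Infusions from Day 22 on and strictly before the limit: 0.
- From the Day 15 dose: 15 + 14 = Day 29. Infusions before the limit: 1 (Day 22).

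Visit windows of 2 days either way widen these counts to 0–1 and 1–2, so each rises by at most 1.

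**Step 3. How likely is such an event?** Section 1.4 reports one drug-related severe event in trial 1280.1, a pulmonary haemorrhage. It gives 48 patients for that trial and 33 for 1280.2; 48 + 33 = 81, which matches the stated total. So 0 of 48 patients had a drug-related severe AST/ALT or glucose event.

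One-sided exact 95% upper limit: 1 − 0.05^(1/48) = 0.0605, or 6.1%. Applied to the maximum of 24 patients: 0.0605 x 24 = 1.45. This bounds any such event at any time. The gap also needs the event to be present at a Day 1, not yet DLT-equivalent and not held by judgement, so 1.45 overstates it.

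**The case against.** The strongest reply is that nobody is made to give the dose. A reader might infer from 4.1.3.5 that a patient with a severe ALT rise must be infused. The documents do not support that. The third criterion brings in 3.3.4.1, whose examples are "undue toxicity, pregnancy, surgery, concomitant diagnoses, concomitant therapies, administrative reasons", and 4.1.3.7 allows interruption at any time. The closing paragraph of 4.1.3.2 also lets the investigator and sponsor agree case by case that an event is a DLT. Its wording names grade 2, but a worse event could plausibly be treated the same way. All of this stands, and all of it is judgement. It limits the consequence without supplying a limit.

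Further objections narrow the point:

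- **Bilirubin is not exempt.** Drug-related liver injury with raised bilirubin can fail 4.1.3.5 below the DILI trigger. The liver gap is isolated AST/ALT only.
- **The other listed terms are not shown to be gaps.** Skin, electrolyte and fatigue events have their own DLT conditions, and infusion reactions are managed under 4.2.1.1.
- **Treatment-responsive hyperglycaemia** is deliberately tolerated by 4.1.3.2 and should stay so.
- **A count of two doses** is tempting but needs the clock to start at the very infusion whose release is in question. For an event already present, an earlier dose is the natural start.
- **Little exposure may remain.** The rollover part is excluded. Section 2.3 records the sponsor's recommendation of 19 October 2021 to stop all treatment, and the current version is dated 29 April 2022. The documents do not show that anyone is still treated under 4.1.3.5.

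The last objection reduces the practical benefit more than any other. It does not change what the rule says.

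**Conclusion.** The point holds in narrow form. Section 4.1.3.5 states a permissive rule: isolated AST/ALT rises and hyperglycaemia pass the recovery criterion at any grade. For a new drug-related grade 3 or higher event of either kind, only judgement holds the Day 1 infusion until the event becomes a DLT or DLT-equivalent.

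The size is small. Nominally 0 or 1 full dose precedes the 14-day limit. The likelihood bound of 6.1% assumes that the 1280.1 rate, observed over mixed doses, applies to Japanese patients at 750 to 1400 mg. It covers drug-related severe events only.

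A reader might also infer that the MTD is compromised. It is not: 4.1.3.5 governs release of doses from Cycle 2 onwards and neither defines nor counts DLTs. This is a cheap improvement to a safety rule. Confidence is high in the reading of the text and lower in how much benefit remains.

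**What to change.** Amend 4.1.3.5 as follows.

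1. The AST/ALT exception applies only below grade 3.
2. The hyperglycaemia exception applies only below grade 3, or where the event is responding to anti-diabetic treatment.
3. An event above these limits is held under 4.1.3.7, within the existing 4 weeks, until grade 2 or lower or baseline. It does not lead to immediate discontinuation.
4. Treatment then resumes at the same dose. If the event has meanwhile become DLT-equivalent, 4.1.3.6 applies instead.

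The cost is a wording amendment plus an occasional missed or delayed dose and a repeat laboratory test. AST, ALT and glucose are already scheduled at Visit 1 of every cycle, and results up to 2 days old may be used. DLT definitions, dose levels and analyses do not change.

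Two limits of the fix should be stated openly. Infusions on Days 8 and 15 stay under the judgement in 4.1.3.7. A non-listed grade 2 event would still end treatment where a severe AST/ALT rise is only held.
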